7.3.3 Death

Death as such is the outcome of a SAE and should not be used as the SAE term itself. The cause of death should be recorded as the SAE term instead. When available, the autopsy report will be provided to the Sponsor.

Grade 5 should be used for events which lead immediately (within 24 hours) and directly to death, and grade 4 should be used with outcome death for events which lead to death after a longer time period, and that may also be linked to additional morbidities.

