8.2.2 Safety Analyses

AEs, SAEs, deaths, laboratory evaluations, dose delays/skipped/reductions and study drug discontinuations due to AEs will be tabulated in a descriptive way. Counts and percentages will be used for categorical variables, and summary tables will be used for continuous variables. Exploratory Fisher's exact tests will be performed to compare grade 4 or grade 3/4 between treatment arms.

An interim safety analysis, performed when 40 patients are enrolled in the PM01183 arm (Arm A), will test if the addition of primary CSF prophylaxis might be necessary. With the information available at that time, a Bayesian test assuming non-informative prior distribution will be done to assess the null hypothesis of febrile neutropenia $\leq 20\%$ *versus* the alternative hypothesis of febrile neutropenia $>20\%$. If the probability associated with the alternative hypothesis is higher than 50% (e.g., 8 cases out of 40 patients), the addition of primary CSF prophylaxis would be considered necessary.

At the time of the interim safety analysis, recruitment in the control arm (Arm B, PLD and topotecan) is also expected to be 40 patients.

The IDMC may request to review other preliminary safety/efficacy parameters, but no claim of superiority will be done; therefore, no type I/II error corrections will be applied.

A safety evaluation will also be performed by the IDMC as part of the futility analysis, when a total of 210 patients are included.

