7 STATISTICAL METHODOLOGY FOR SAFETY

7.1 *Toxicity and Adverse Events*

Patients will be evaluable for safety if they have received any partial or complete treatment infusion. All AEs will be graded according to the NCI-CTCAE v.4. Treatment delays, dose reduction requirements and reason for treatment discontinuation will be monitored throughout the study.

The safety profile of patients will be monitored throughout the treatment and up to 30 days after the last treatment infusion (end of treatment, EOT), or until the patient starts a new antitumor therapy or until the date of death, whichever occurs first.

Any AEs will be coded using to the Medical Dictionary for Regulatory Activities (MedDRA). Treatment-related AEs will be followed, whenever possible, until recovery to at least grade 1 or stabilization of symptoms, whenever possible.

Summary of overall AEs will be done by body system and preferred term, by severity (worst toxicity grade) and by relationship. Tables will be sorted by body system/preferred term.

A frequency table will be made for the AEs leading to cycle delay, dose reduction, skipped dose (topotecan only), or withdrawal of study medication. AEs leading to permanent treatment stop and AEs with outcome of death will also be presented by relationship to drug.

Exploratory Fisher's exact tests will be performed to compare the incidence of grade 4 or grade 3/4 AEs between treatment arms.

7.2 *Clinical Laboratory Evaluation*

Laboratory results will be classified according to the NCI-CTCAE v.4.

The worst grade per patient will be tabulated during overall treatment and per cycle for hematology values [white blood cells (WBC), absolute neutrophil count (ANC), lymphocyte count, platelet count and hemoglobin] and for the following biochemistry tests: alanine aminotransferase (ALT), aspartate aminotransferase (AST), total bilirubin, alkaline phosphatase (AP), creatine phosphokinase (CPK), creatinine, glucose, sodium, potassium and albumin.

Exploratory Fisher's exact tests will be performed to compare the incidence of grade 4 or grade 3/4 laboratory evaluations between treatment arms.

7.3 *Physical Examination Findings*

Tables summarizing the performance status (PS), height, body weight and BSA (according to the Dubois and Dubois formula) at baseline will be prepared.

In addition, changes in the ECOG PS and body weight of each patient during the treatment compared to baseline will be presented.

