12.2.2 Display of Adverse Events

Table 12.2.2.1 Summary of adverse events

Category	PM01183	Control
	N (%)	N (%)
Number of patients with any AE		
Number of patients with any drug-related AE		
Number of patients with any grade 3/4 AE		
Number of patients with any grade 4 AE		
Number of patients with any grade 3/4 drug-related AE		
Number of patients with any grade 4 drug-related AE		
Number of patients with any SAE in DB		
Number of patients with any drug-related SAE in DB		

Category	PM01183	Control
	N (%)	N (%)
Number of patients with any grade 3/4 SAE in DB		
Number of patients with any grade 4 SAE in DB		
Number of patients with any grade 3/4 drug-related SAE in DB		
Number of patients with any grade 4 drug-related SAE in DB		
Number of patients with death associated with AEs		
Number of patients with death associated with drug-related AEs		
Number of patients with treatment discontinuations associated with AEs		
Number of patients with treatment discontinuations associated with drug-related AEs		
Number of patients with delays associated with AEs		
Number of patients with delays associated with drug-related AEs		
Number of patients with reductions associated with AEs		
Number of patients with reductions associated with drug-related AEs		

Table 12.2.2.2 Drug-related adverse events. Worst grade by patient

Table 12.2.2.3 Drug-related adverse events. Worst grade by cycle

Table 12.2.2.4 Adverse Events regardless of relationship. Worst grade by patient

Table 12.2.2.5 Adverse Events regardless of relationship. Worst grade by cycle

Category/MedDRA Code		Grade																			
		PM01183										Control									
		1		2		...		G≥1		G≥3		1		2		...		G≥1		G≥3	
		N	%	N	%	N	%	N	%	N	%	N	%	N	%	N	%	N	%		
Blood and lymphatic system disorders																					
	Anaemia NOS																				
	...																				
Cardiac disorders																					
	Arrhythmia NOS																				
	...																				
...																					

Listing 12.2.2.6 Drug-related grade 3/4 adverse events. Worst grade by cycle

Treatment arm*	Patient id.	Cycle	SOC Name	PTCode	Grade

*PM01183, PLD or Topotecan

Listing 12.2.2.7 Grade 3/4 adverse events regardless of relationship. Worst grade by cycle

Treatment arm*	Patient id.	Cycle	SOC Name	PTCode	Grade

*PM01183, PLD or Topotecan

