12.2.3 Evolution of Signs and Symptoms during the Treatment

Worst grade of signs and symptoms present at baseline in a percentage $\geq 10\%$ or grade ≥ 3 and their evolution during treatment will be shown regardless of relationship.

Table 12.2.3.1 Shift of signs and symptoms during treatment

12.3 Serious Adverse Events and Deaths.

12.3.1 *Serious Adverse Events*

Table 12.3.1.1 Drug-related serious adverse events. Worst grade by patient

Table 12.3.1.2 Drug-related serious adverse events. Worst grade by cycle

Table 12.3.1.3 Serious adverse events regardless of relationship. Worst grade by patient

Table 12.3.1.4 Serious adverse events regardless of relationship. Worst grade by cycle

Listing 12.3.1.5 Drug-related grade 3/4 serious adverse events. Worst grade by cycle

Treatment arm*	Patient id.	Cycle	SOC Name	PTCode	Grade

*PM01183, PLD or Topotecan

Listing 12.3.1.6 Grade 3/4 serious adverse events regardless of relationship. Worst grade by cycle

Treatment arm*	Patient id.	Cycle	SOC Name	PTCode	Grade

*PM01183, PLD or Topotecan

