12.5 Subgroup Analyses Related to Safety

Information for laboratory abnormalities comes from hematology/biochemistry forms and not from AE form.

Table 12.5.1 Worst grade 3/4 by patient in special subgroups (Age)

Laboratory abnormalities/ drug-related AEs	<65 years-old			≥65 years-old		
	No. of patients evaluated	Grade 3/4	%	No. of patients evaluated	Grade 3/4	%
PM01183						
Thrombocytopenia						
Neutropenia						
ALKP						
Bilirubin						
SGOT-AST						
SGPT-ALT						
CPK						
Nausea						
Vomiting						
Fatigue						
Other*						
Control						
Thrombocytopenia						
Neutropenia						
ALKP						
Bilirubin						
SGOT-AST						
SGPT-ALT						
CPK						
Nausea						
Vomiting						
Fatigue						
Other*						

*Any drug-related toxicity present in >=5% of patients in any group.

Table 12.5.2 Worst grade 3/4 by cycle in special subgroups (Age)

Laboratory abnormalities/ drug-related AEs	<65 years-old			≥65 years-old		
	No. of cycles evaluated	Grade 3/4	%	No. of cycles evaluated	Grade 3/4	%
PM01183						
Thrombocytopenia						
Neutropenia						
ALKP						
Bilirubin						
SGOT-AST						
SGPT-ALT						
CPK						
Nausea						
Vomiting						
Fatigue						
Other*						
Control						
Thrombocytopenia						
Neutropenia						
ALKP						
Bilirubin						
SGOT-AST						
SGPT-ALT						
CPK						
Nausea						
Vomiting						
Fatigue						
Other*						

*Any drug-related toxicity present in $\geq 3\%$ of cycles in any group.

Table 12.5.3 Worst grade 3/4 by patient in special subgroups (Race)

Laboratory abnormalities/ drug-related AEs	White			Other		
	No. of patients evaluated	Grade 3/4	%	No. of patients evaluated	Grade 3/4	%
PM01183						
Thrombocytopenia						
Neutropenia						
ALKP						
Bilirubin						
SGOT-AST						
SGPT-ALT						
CPK						
Nausea						
Vomiting						
Fatigue						
Other*						
Control						
Thrombocytopenia						
Neutropenia						
ALKP						
Bilirubin						
SGOT-AST						
SGPT-ALT						
CPK						
Nausea						
Vomiting						
Fatigue						
Other*						

*Any drug-related toxicity present in $\geq 5\%$ of patients in any group.

Table 12.5.4 Worst grade 3/4 by cycle in special subgroups (Race)

Laboratory abnormalities/ drug-related AEs	White			Other		
	No. of cycles evaluated	Grade 3/4	%	No. of cycles evaluated	Grade 3/4	%
PM01183						
Thrombocytopenia						
Neutropenia						
ALKP						
Bilirubin						
SGOT-AST						
SGPT-ALT						
CPK						
Nausea						
Vomiting						
Fatigue						
Other*						
Control						
Thrombocytopenia						

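### The SAP mixes grade 3/4 with grade ≥3 cut-offs, so an adverse event that is fatal within 24 hours counts as severe in some outputs and not in others

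*Protocol*

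**What the plan says.** Protocol 7.3.3 grades a fatal event by how fast death follows. It reads "Grade 5 should be used for events which lead immediately (within 24 hours) and directly to death, and grade 4 should be used" and goes on "with outcome death for events which lead to death after a longer time period".

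Two families of severity cut-off follow.

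- **Without grade 5.** Protocol 8.2.2 plans exploratory Fisher tests to "compare grade 4 or grade 3/4 between treatment arms". SAP 7.1 repeats this: "compare the incidence of grade 4 or grade 3/4 AEs between treatment arms". Table 12.2.2.1 in SAP 12.2.2 has eight severity rows, such as "Number of patients with any grade 3/4 AE", and all eight are grade 3/4 or grade 4. Listings 12.2.2.6, 12.2.2.7, 12.3.1.5 and 12.3.1.6 carry the same limit, for example "Listing 12.3.1.5 Drug-related grade 3/4 serious adverse events. Worst grade by cycle". So do Tables 12.5.1 to 12.5.8, which begin with "Table 12.5.1 Worst grade 3/4 by patient in special subgroups (Age".
- **With grade 5.** Tables 12.2.2.2 to 12.2.2.5 and Tables 12.5.9 to 12.5.12 (against PLD and against topotecan) have a G≥3 column. The Fisher shells, Tables 12.4.4.10 and 12.4.4.11, split at <3 against ≥3 and at <4 against ≥4.

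Fatal events also have their own outputs: two death rows in Table 12.2.2.1, cause of death in Table 12.3.3.1, and Listings 12.3.3.2 (deaths) and 12.3.3.3 (fatal adverse events).

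**The concern.** Two patients can die of the same toxicity and receive different grades solely because one died sooner. That is harmless if every severe-event output is open at the top. It is not harmless where the output stops at grade 4: the slower death is counted as severe and the faster one is not. In outputs built on worst grade, an event that starts at grade 3 and ends at grade 5 also leaves the 3/4 cell for its term.

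What is at stake is whether the severe-toxicity figures agree with one another. Two programmers who both follow the SAP could report different numbers of patients with severe events. A reader comparing the summary table with the per-term tables, or the age subgroups with the PLD comparison, would be comparing different definitions. The Fisher tests are described one way in the text and laid out another way in the shells, so the SAP does not settle which is to be run.

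**Working it through.** The plan states no figure to reproduce here. The check is whether grade 5 falls inside each cut-off.

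| Place | Cut-off | Grade 5 included? |
|---|---|---|
| Protocol 8.2.2 and SAP 7.1, Fisher text | 4; 3/4 | No, read literally |
| Tables 12.4.4.10–11, Fisher shells | ≥3; ≥4 | Yes |
| Table 12.2.2.1, eight severity rows | 3/4; 4 | No |
| Tables 12.2.2.2–5, per term | G≥3 | Yes |
| Listings 12.2.2.6–7 and 12.3.1.5–6 | 3/4 | No |
| Tables 12.5.1–8 (age, race, prior lines, region) | 3/4 | No |
| Tables 12.5.9–12 (PLD, topotecan) | G≥3 | Yes |

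**Two example events.** Take one drug-related adverse event that kills at 20 hours and another that kills at 30 hours. Under 7.3.3 the first is grade 5, provided it led directly to death, and the second is grade 4 with outcome death. The second qualifies on grade for every row of the table. The first qualifies only for the three rows marked Yes. Both appear in the death rows and in Listing 12.3.3.3.

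**Size.** The documents give neither the rate of fatal adverse events nor the time to death, so both are assumptions. With 420 patients randomized 1:1 there are about 210 per arm.

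- Low end: 1% fatal, a quarter within 24 hours: 210 × 0.01 × 0.25 = 0.5 patients per arm.
- High end: 3% fatal, a half within 24 hours: 210 × 0.03 × 0.50 = 3.2 patients per arm.

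One patient is 1/210 = 0.5% of an arm. She leaves the any-grade-3/4 row only if she has no other grade 3/4 event. The fatal event itself leaves the grade 3/4 listings in any case.

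**Effect on a test (illustration with assumed counts).** Suppose one term has 12 of 210 patients at grade 3/4 in each arm, plus k grade 5 patients in Arm A only. Two-sided Fisher p-values:

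| k | Grade 3/4: 12 vs 12 | Grade ≥3: 12+k vs 12 | Grade ≥4: 4+k vs 4 |
|---|---|---|---|
| 1 | 1.00 | 1.00 | 1.00 |
| 2 | 1.00 | 0.84 | 0.75 |
| 3 | 1.00 | 0.69 | 0.54 |
| 5 | 1.00 | 0.44 | 0.26 |
| 8 | 1.00 | 0.20 | 0.07 |

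The last column assumes 4 of 210 at grade 4 in each arm. The closed cut-off is blind to the grade 5 excess at every k. Even so, the choice alters the picture only if several grade 5 events fall in one arm, which is beyond the range above for a single term.

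**The case against.** The strongest reply is that nothing is hidden. Fatal adverse events are tabulated by outcome, in all and by relationship to drug, and the death rows sit in the same summary table as the grade 3/4 rows. Listing 16.2.7 shows grade and outcome for every event. On this view, separate lines for grade 3/4 and for death are a display choice. The main per-term tables and the Fisher shells already include grade 5. The tests are exploratory, and no decision hangs on the cut-off: the interim rule on primary CSF prophylaxis counts febrile neutropenia without a grade limit (Protocol 8.4, SAP 5.2.2).

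The reply has further force for the subgroup tables. Seven of the ten named rows in Tables 12.5.1–12.5.8 are laboratory parameters, and SAP 12.5 takes laboratory abnormalities from the laboratory forms, so the rule for fatal adverse events does not touch them. The remaining named rows are nausea, vomiting and fatigue. The row for other toxicities is limited to drug-related events in at least 5% of patients or 3% of cycles in any group, so a rare event such as sepsis would usually not appear at all.

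Most of this stands, and it limits the size of the problem. It does not remove the inconsistency. A display choice would be applied uniformly, whereas here the closed and open cut-offs alternate within section 12.5 and within section 12.2.2, and the Fisher text disagrees with its shells. A separate line for death also does not explain why a death at 30 hours is in both the severe rows and the death rows while a death at 20 hours is only in the latter. The death table is broken down by arm and control drug, not by age, race, prior lines or region, so it does not fill the gap in the subgroup displays.

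**Conclusion.** The SAP's severity cut-offs are inconsistent. Combined with the 24-hour grading rule, they place a rapidly fatal event inside some severe-event outputs and outside others, while a slower fatal event is inside all of them. The contradiction between the SAP 7.1 text and Tables 12.4.4.10–11 is plain on the page. The rest assumes that the outputs are programmed as titled.

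The effect is probably small, about 0.5 to 3 patients per arm of 210, under assumed rates that the documents neither give nor exclude. The primary endpoint is unaffected.

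A reader might infer three stronger things that the documents do not support.

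- That the fastest deaths drop out of the safety report. They do not: they have their own rows and listings, and a patient can still count as severe through another event.
- That the significance tests exclude them. The text suggests so and the shells say otherwise, so this is an unresolved contradiction, not a settled exclusion.
- That most fatal events will carry grade 4, or that subgroup rates of infrequent events will be materially distorted. Nothing in the documents gives the timing of fatal events, and most named subgroup rows come from laboratory data.

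**What to change.** In SAP 7.1, Table 12.2.2.1, Tables 12.5.1–12.5.8 and Listings 12.2.2.6–7 and 12.3.1.5–6, replace grade 3/4 with grade ≥3 and grade 4 with grade ≥4. That aligns them with the Fisher shells and the per-term tables. Go on counting fatal adverse events by the outcome field, which is already collected (Listing 13.1.30). Grade 5 should not stand in for all fatal events, because under 7.3.3 it covers only the rapid ones.

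The grading rule in Protocol 7.3.3 need not change. The sentence in Protocol 8.2.2 shares the wording, but Protocol 8.2 leaves specific details to the SAP, so the correction can be made there.

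The cost is a wording change in the SAP and its shells, with no new data. The one drawback for the sponsor is that stated severe-event rates may become slightly less favourable.

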7.3.4 Life-threatening Event

Any event in which the patient was at risk of death at the time of the event is considered life-threatening; it does not refer to an event which hypothetically might have caused death if it were more severe.

7.3.5 Hospitalization or Prolongation of Hospitalization

Any AE requiring hospitalization (or prolongation of hospitalization) that occurs or worsens during the course of a patient’s participation in a clinical trial must be reported as a SAE unless exempted from SAE reporting (see Section [7.4.2](#)). Prolongation of hospitalization is defined as any extension of an inpatient hospitalization beyond the stay anticipated/required for the initial admission, as determined by the Investigator or treating physician.

Hospitalizations that do not meet criteria for SAE reporting are:

- a. Reasons described in protocol [e.g., investigational medicinal product (IMP) administration, protocol-required intervention/investigations, etc.]. However, events requiring hospitalizations or prolongation of hospitalization as a result of a complication of therapy administration or clinical trial procedures will be reported as SAEs.
- b. Hospitalization or prolonged hospitalization for technical, practical or social reasons, in absence of an AE.
- c. Pre-planned hospitalizations: any pre-planned surgery or procedure must be documented in the source documentation. Only if the pre-planned surgery needs to

be performed earlier due to a worsening of the condition, should this event (worsened condition) be reported as a SAE.

Other situations that MUST NOT be considered as hospitalizations are the following:

- d. An emergency visit due to an accident where the patient is treated and discharged.
- e. When the patient is held 24 hours for observation and finally is not admitted.
- f. Planned treatments at sites not associated to a hospital and generally considered as minor surgical procedures (i.e., laser eye surgery, arthroscopy, etc.).

7.3.6 Unlisted/Unexpected Adverse Event

An AE, the nature or severity of which is not consistent with the applicable reference safety information.

The Sponsor will use as the reference safety information for the evaluation of listedness/expectedness the IB for lurbinectedin (PM01183) and the Reference Safety Information for PLD and topotecan.

7.3.7 Adverse Reactions

All untoward and unintended responses to an investigational medicinal product related to any dose administered. This definition covers also medication errors and uses outside what is foreseen in the protocol, including overdose, lack of efficacy, misuse and abuse of the product.

7.3.8 Adverse Events Related to the Study Drug

An AE is considered related to a study drug/IMP if the Investigator's assessment of causal relationship to the IMP(s) is "Y (yes)" (see Section [7.3.10](#)).

The Investigator will assess the causal relationship of the IMP(s) to the SAE.

The Sponsor may also consider related to the study drug(s)/IMP(s) those events for which the Investigator assesses the causal relationship with the IMP(s) as "Uk (unknown)" when it cannot rule out a role of the IMP(s) in the event.

7.3.9 Expedited Reporting

The Sponsor is responsible for the appropriate expedited reporting according to the applicable legislation.

7.3.10 Assessment of Causal Relationship to the Study Drug

The Investigator must provide an assessment of the causal relationship of each SAE to the clinical trial IMP(s) according to the following scale:

- Y** There is a reasonable possibility that the IMP(s) caused the SAE.
- N** There is no reasonable possibility that the IMP(s) caused the SAE and other causes are more probable.
- Uk** (Unknown). Only to be used in special situations where the Investigator has insufficient information (i.e., the patient was not seen at his/her center) if none of the above can be used.

7.4 ADVERSE EVENTS REPORTING PROCEDURES

7.4.1 Reporting Adverse Events

The Sponsor will collect AEs until 30 days after administration of the last dose of study drug(s)/IMP(s) or until the start of a new antitumor therapy or until the date of death, whichever occurs first. All AEs suspected to be related to the study drug/IMP must be

followed-up after the time of therapy discontinuation until the event or its sequelae resolve or stabilize at an acceptable level to the Investigator and the Sponsor.

All AEs, including medication errors and uses outside what is foreseen in the protocol, must be recorded in English using medical terminology in the source document and the CRF. Whenever possible, the Investigator will record the main diagnosis instead of the signs and symptoms normally included in the diagnoses.

Investigators must assess severity (grade) of the event following the NCI-CTCAE v. 4 and assign a relationship to each study drug(s)/IMP(s); and pursue and obtain information adequate both to determine the outcome and to assess whether it meets the criteria for classification as a SAE requiring immediate notification to Pharma Mar S.A. or its designated representative. The Investigator must provide any relevant information as requested by the Sponsor in addition to that on the CRF.

Abnormal laboratory tests occurring during the study should only be recorded in the AE section of the CRF if the disorder:

- Is associated with clinically significant symptoms, and/or
- Leads to a change in study dosing or discontinuation from the study, significant additional concomitant drug treatment or other therapy, and/or
- Leads to any of the outcomes included in the definition of a SAE.

Otherwise laboratory results should be reported in the corresponding section of the CRF (e.g. biochemistry, hematology).

All episodes of febrile neutropenia must always be reported within 24 hours following the same procedure for reporting SAEs (see Section [7.4.2](#)), including episodes that occurred in patients without seriousness criteria. For these cases, the seriousness criterion should be reported as a medically significant event.

